#### 852 4.3.2. Participant Selection

853

854 See Section 4. for general eligibility criteria. Further details of inclusion and exclusion 855 criteria for potential LDLT donors are given below.

856

#### **Inclusion Criteria:** 857

858

859 1. LDLT Donors: Following the formal donor evaluation, the decision to perform the donor surgery is entirely at the discretion of the transplant center and the donor. Once 860 861 a donor is accepted into the donor cohort, s/he will be asked for consent to participate 862 in the study of donor long-term outcomes, morbidity and quality of life.

863 2. LDLT Donor Controls: Some potential donors who fail to donate will become 864 controls for the long-term donor study. LDLT donor controls will also be asked to 865 consent to study their long-term outcomes. Failure to donate and subsequent 866 inclusion in the donor control cohort can be based upon recipient issues (condition worsening or availability of DDLT) or donor health issues. In the latter case, the 867 donors may have mild to moderate medical conditions that precluded donation, but 868 which are not expected to impact their long-term quality of life or alter the potential 869 870 donor's natural history of survival/disease development compared to the normal 871 population. We will also utilize donor candidates from the Retrospective Study who 872 have not donated as donor controls.

- 873 a. Assessment of donor controls will be limited to collection of morbidity and 874 survival information, administration of Quality of Life and Informed Consent 875 instruments post-donation. 876 3. The event that will switch a donor from the pre-donation assessment regimen to the 877 donor post-donation assessment regimen or the donor control post-event assessment 878 regimen is the occurrence of one of the following events (whichever happens first): 879 a. Donation 880 b. Donor ruled out (but only with mild co-morbid conditions as outlined above) 881 c. Donor withdraws 882 d. Recipient dies e. Recipient is removed from the waiting list 883 884 f. Recipient receives DDLT 885 886 **Exclusion Criteria:** 887
- 888 1. Donors who are rejected due to serious health conditions will not be included in the cohort. The donor control exclusion criteria would include, but would not be limited 889 890 to abnormalities identified during formal evaluation, which preclude donation and 891 alter the potential donor's natural history of survival/disease development compared 892 to the normal population.
- 893
- 894 4.3.3. Data Elements
- 895 A. Potential Donor Data Collection
- 896 1. Donor Evaluation
- 897 2. Donor Demographic Form
- 898
- 899 B. Donation and post-donation follow-up
- 900 1. Donor Intraoperative Data
- 901 2. Donor Post-Surgical Morbidity
- 902 3. Donor Hospitalization data
- 903 4. Donor OOL Assessment
- 904 5. Donor Survival
- 905
- 906

#### **4.3.4.** Sample Size and Power Calculations

907 This analysis is based on comparisons of donors and donor controls over time in the 908 standardized questionnaire scores. For the power calculations, we will consider the 909 power to detect differences between donors and controls at a single time point based on a 910 two-sample t-test. Power for the proposed repeated measures analysis will be greater, 911 although the amount of improvement will depend on the correlation between successive 912 measures on the same individual, which is not known at this time. We assume that the 913 Cohort Study will yield 360 LDLT donors and 710 donor controls

914

915 Assuming a 2-sided significance level of 0.05, we will have 87% power to detect an

916 effect size of 0.20 (i.e., a difference of 0.20 standard deviations in any given measure

917 between donors and donor controls). Cohen has suggested that an effect size of 0.25 is a 918 small effect, so we will have the power to detect quite small differences between donors 919 and donor controls.

#### 920 4.3.5. Statistical Analysis

921 The first goal of the analysis is to estimate the mortality and morbidity after liver

922 donation. Although we expect and hope that no donor mortality occurs, if any does, then

923 probability of mortality will be estimated using the Kaplan-Meier estimator with

924 confidence intervals at specific points such as one and two years. With this estimator, the 925 probability of donor death at any time point during post-surgery follow-up can be given.

926

927 Donor morbidity will be estimated as a proportion of donors with each reported

928 complication at relevant time points after surgery. Complications reported will include

bile leak, primary non-function, graft failure, pneumonia, and urinary tract infection, as

930 well as any complication requiring hospital admission, re-operation, or other intervention.

931 Confidence intervals for each proportion will be given. We will also report follow-up

932 outcomes including wound healing, pain medications, blood laboratory values, and the

proportion of patients who returned to work/school. Some attempt will be made to

correlate complications with patient characteristics and operative procedures, but anysuch analyses will be limited by the quality of available data.

- 936 The second goal of the analysis is to estimate the long-term health-related QOL of donors
- 937 compared to a control population. The analysis will employ repeated measures

938 regression analysis, implemented using SAS Proc Mixed software. Outcome measures

- will be validated scales from established QOL instruments. Mean differences over time
- between donors and controls will be estimated. Possible changing effects over time will
- be tested using time by transplant group interactions. These analyses will be adjusted for
- other variables predictive of health-related QOL, such as age, gender, and baseline
  comorbidities. The covariance structure of the repeated measures over time will be

investigated using a full model prior to any covariate reduction. Donors recruited from
the A2ALL Retrospective Study will initially be analyzed separately, and then compared
with donors from the Cohort Study. If the two donor groups are similar, they may be
pooled to compare with the control group. If the two donor groups are not similar, they

- 947 pooled to compare with the control group. If the two donor groups are not similar, they 948 will be analyzed as separate groups. We could then estimate any change in donor quality
- of life over calendar time, or by experience at the transplant center, due to improvements
- 950 in transplant methods or surgeon skill.
- 951

The analysis of pain scores will parallel the repeated measures analysis described above.

However, at each time point we will also collect data on the patient's expected future

pain. We will compare the predicted future pain with the pain score actually obtained at

- 955 the next questionnaire completion. In addition to the standardized scales, individual
- 956 questions from the A2ALL Donor Survey will also be analyzed, primarily using
- 957 descriptive statistics. Covariate predictors of some of these outcomes may be
- 958 investigated using linear or logistic regression.
- 959

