258 We will recruit additional patients (potential and actual recipients, actual donors and 259 donor candidates who have not yet donated, but are early enough in their donation evaluation so that it is unclear whether they will go on to donation) from the A2ALL 260 Retrospective Study (Grant 5 R01 DK62498-02) who are still alive at the start of the 261 262 cohort study. We will also recruit those patients (recipients, recipient candidates, donors and donor candidates still being evaluated) whose donor evaluation occurred between the 263 264 end of the Retrospective Study (2/28/2003) and the start of this prospective study at each 265 site. Another cohort who will be approached for participation are those subjects 266 (recipient candidates) whose date of donor evaluation occurs more than 4 weeks from the 267 time the patient is approached. These subjects will be consented, despite the fact that they will have already passed the entry milestone of the living donor evaluation. Donor 268 269 candidates who have not yet donated will be utilized as donor controls. Data from time 270 of listing to cohort study enrollment will be collected retrospectively. Subjects will be 271 followed prospectively according to the cohort study schedule of events, starting at the 272 time of their enrollment. This enables a seamless capture of data and analysis of living 273 donor transplantation from its inception into the future. Revised Cohort Protocol 031006 Page 6 of 56 A2ALL: Adult-to-Adult Living Donor Liver Transplant Cohort Study Protocol Version Date: Amendment II, March 10, 2006

[figure not shown]

Figure 1: Flow Diagram for Entry of LDLT and DDLT Recipients into the Study

279

280

281 The table below summarizes the populations that will be investigated in this study for

each specific aim of the cohort study. Eligibility criteria for these populations are given
below.

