#### 4.2.4. Sample Size and Power Calculations

Estimation of proportions of donor complications will be made using 95% confidence
intervals (CI) based on the binomial distribution. Assuming 660 donors, 95% CI widths
will be no larger than +/- 0.04.

726

Comparisons of recipient complications after LDLT and DDLT transplants will be based
on chi-square tests of equality of proportions. Assuming n=660 LDLT, n=550 DD, and
alpha=0.05, we will have 83% power to detect a difference in the proportion of bile leaks,
for example, of 0.18 in the DDLT group versus 0.25 in the LDLT group (a difference of

731 0.07). Physician estimates of this difference are closer to 0.20, so power is more than

- 731 0.07). Physician estimates of this difference are closer to 0.20, so power is more than
   732 sufficient for this endpoint. If we more conservatively assume complication proportions
- near 0.5, we will have 93% power to detect a difference of 0.10 (such as 0.45 versus
- 734 0.55).

#### 735

For comparing hospitalization between LDLT recipients and non-recipients we consider the number of hospital days in one year. Although the analysis will take into account the possibility that some patients may be included in both groups, both pre- and post-LDLT, the power calculations consider a similar but simplified design based on a two-sample ttest (2-sided, alpha=0.05), assuming 660 LDLT recipients and 710 non-recipients. We have no preliminary data on means or standard deviations (s.d.s) for number of hospital days in a year, but assuming a fairly large s.d. of 25 days, we will have 95% power to

- days in a year, but assuming a fairly large s.d. of 25 days, we will have 95% power to detect a difference of 5 days (effect size = 0.20 s.d.) between LDLT and non-LDLT
- 744 groups.
- 745

746

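### Section 4.3.5 estimates donor mortality only if a death occurs, so the expected result of zero deaths comes with no estimate and no upper limit on the risk

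*Protocol*

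**What the plan says.** Protocol section 4.3.5 opens: "The first goal of the analysis is to estimate the mortality and morbidity after liver" donation. The next sentence sets the condition: "Although we expect and hope that no donor mortality occurs, if any does, then" the "probability of mortality will be estimated using the Kaplan-Meier estimator with" "confidence intervals at specific points such as one and two years". The type of interval is not named, and nothing is laid down for the case of no deaths.

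Morbidity is handled differently. The same section promises a confidence interval for the proportion with each complication, without any condition. Section 4.2.4, which sits under the recipient aim, adds that donor complication proportions will have 95% "intervals (CI) based on the binomial distribution. Assuming 660 donors, 95% CI widths" of at most +/- 0.04. Both statements concern complications; neither covers mortality.

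Two donor counts appear. Section 4.3.4 assumes that the "Cohort Study will yield 360 LDLT donors and 710 donor controls". Section 4.2.4 uses 660, which matches the 300 Retrospective plus 360 Cohort living donor transplants in section 4.1.4. Section 4 (Investigational Plan) also recruits people from the A2ALL "Retrospective Study (Grant 5 R01 DK62498-02) who are still alive at the start of the" cohort study, donors among them.

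**The concern.** A rule that estimates a risk only after an event has been seen says nothing in the case where a reader most needs a number. No deaths among a few hundred donors is compatible with a true risk of several per thousand, and only an upper confidence limit shows that. The Kaplan-Meier method does not fill the gap: with no deaths the survival estimate stays at 1 and Greenwood's variance is 0.

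The stake is set out in the protocol itself. Section 2 ties public interest in donor safety to a donor death in 2002, section 3 makes the donor a primary objective, and section 4.3 says these analyses are needed so that prospective donors can consent on an accurate picture of the risk. A report of no deaths with no upper limit can be read as no risk.

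A second, smaller matter arises if one or two deaths occur. Kaplan-Meier intervals of different types then differ widely, and the protocol does not say which is meant.

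**Working it through.** **Inputs.** Donors: 360 (section 4.3.4) and 660 (section 4.2.4). Confidence level: 95%, two-sided. Expected deaths: none (section 4.3.5). Assumption: every donor is followed to the time point, so that the Kaplan-Meier estimate equals deaths/n. Censoring would widen the limits.

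**The plan's own precision figure.** The half-width at p = 0.5 with n = 660 is 1.96 x sqrt(0.25/660) = 0.0381 (exact method: 0.0388). The stated +/- 0.04 is reproduced. It is a worst case for complication proportions and is of no use for a risk near zero.

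**Zero deaths.** Kaplan-Meier: S = 1, Greenwood variance = 0, width = 0. Exact two-sided 95% upper limit = 1 - 0.025^(1/n):

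- n = 360: 1 - 0.025^(1/360) = 1.02%, about 1 in 98.
- n = 660: 1 - 0.025^(1/660) = 0.56%, about 1 in 180.

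**How easily zero deaths can arise.** The protocol gives no donor death risk, so a range is assumed. P(no deaths) = (1 - risk)^n:

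| Assumed true risk | n = 360 | n = 660 |
|---|---|---|
| 0.1% | 70% | 52% |
| 0.2% | 49% | 27% |
| 0.3% | 34% | 14% |
| 0.5% | 16% | 4% |

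**One or two deaths.** With p = deaths/n, S = 1 - p and se = sqrt(p(1-p)/n):

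- plain: p +/- 1.96 se
- log-log: 1 - S^exp(-1.96 v) to 1 - S^exp(+1.96 v), where v = se/(S |ln S|)
- exact: Clopper-Pearson (beta quantiles)

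For 1/360: p = 0.278% and se = 0.277%, so the plain interval is 0.278% +/- 0.544%; v = 1.00.

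| Deaths/n | Plain | Log-log | Exact |
|---|---|---|---|
| 1/360 | -0.27% to 0.82% | 0.04% to 1.96% | 0.007% to 1.54% |
| 2/360 | -0.21% to 1.32% | 0.14% to 2.20% | 0.07% to 1.99% |
| 1/660 | -0.15% to 0.45% | 0.02% to 1.07% | 0.004% to 0.84% |

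In 360 donors the plain upper limit after one death (0.82%) is lower than the exact upper limit after none (1.02%). The log-log interval has no negative limit, and its upper limit lies somewhat above the exact one.

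**The case against.** The best defense is that nothing is biased when no deaths occur: the count and the denominator would be known, and anyone can derive the upper limit from them. It can be added that the objectives in section 3.3 speak of significant morbidity and quality of life, so mortality enters only through section 4.3.5. Both points are fair and limit the weight of the concern. They do not remove it, because 4.3.5 names mortality in its first goal and then writes a condition that leaves the expected case without an estimate. That is a stated rule, not a detail left to an analysis plan.

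Three stronger readings are tempting, and the document does not support them.

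- *That any Kaplan-Meier interval fails with one or two deaths.* The protocol names no interval type. A log-log interval is usable, and the choice of type is commonly left to the analysis plan. What stands is only that the result depends on a choice not yet stated.
- *That survivors from the Retrospective Study bias the mortality estimate.* Section 4 requires them to be alive, but this is a recruitment rule. Nothing in 4.3.5 says that they enter the mortality estimate or that their time would run from donation. The rule there for analyzing them separately and then perhaps pooling belongs to the quality-of-life analysis. The bias would arise only if they were counted from surgery without delayed entry.
- *That 660 is simply the denominator.* It is valid only with complete Retrospective records from surgery, deaths included, and the protocol does not show these. If only survivors are added, 660 is too large.

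A fixed-time binomial interval also has a weakness of its own. The donor visit schedule in section 4 allows for loss to follow-up, and section 4.3.1 treats retention as a concern. Kaplan-Meier handles censoring and the binomial does not, so the exact interval should supplement Kaplan-Meier and not replace it.

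**Conclusion.** The point holds in limited form. As written, section 4.3.5 yields no donor mortality estimate and no upper limit if no donor dies, which is the result the protocol expects, and Kaplan-Meier with Greenwood's variance cannot supply one. The size of what would go unreported is an upper limit of 1.02% for 360 donors, assuming complete follow-up. The figure of 0.56% for 660 donors applies only under the further condition on the Retrospective records. With one or two deaths the upper limit can roughly double according to interval type (0.82% to 1.96% for one death in 360), so the type needs to be stated. The true risks of 0.1% to 0.5% are illustrative only and the conclusion does not rest on them. The change is worth making, but it does not affect the validity of the other analyses.

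**What to change.** In section 4.3.5:

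1. Delete the condition that a death must occur.
2. Report donor mortality at fixed times (for example 90 days and 1 year) with an exact (Clopper-Pearson) 95% interval among donors whose status at that time is known, whatever the number of deaths, giving the upper limit when there are none.
3. Keep Kaplan-Meier, with a log-log interval, to handle censoring.
4. State the denominator. If donors recruited from the Retrospective Study because they were alive are included, start their time at risk at enrollment. Use 660 as a denominator from surgery only if the Retrospective records are complete, deaths included.

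The cost is a few sentences. Donor survival is already a data element in section 4.3.3, so the cohort donors need no new collection. The small downside is that the exact interval needs known vital status, so the number of donors lost before each time point must be reported alongside it. As an illustration, if 10% of 360 were lost (an assumed figure), 324 would remain and the zero-death limit would be 1 - 0.025^(1/324) = 1.13% instead of 1.02%.

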357 358 359 360 361 362 363	After obtaining the subject's informed consent for participation in the study, the following assessments will be performed according to the visit schedule. Subjects recruited from the A2ALL Retrospective Study will join the cohort visit schedule from whatever clinical point they are at in their transplant or donation experience. Exceptions to this would be informed consent assessments for donors and protocol biopsies for subjects who are undergoing treatment for recurrent HCV post-transplant. Tables summarizing the visit schedules for donors and recipients with accompanying tests and procedures are included as Appendices A and B.
366 367 368	Since the study is primarily an observational investigation, it should be remembered that many of the assessments listed below are included in what is considered standard of clinical care in many institutions, and therefore would not require additional visits or sample collections from the patient.
	Enrollment – Recipients:
373 374 375 376 377 378 379 380 381 382 383 384 385 386 387 388	
 
Medical history
 
Social history
 
Demographic information
 
Physical examination: including weight, blood pressure, etc.
 
Routine laboratory assessment: blood will be drawn to obtain values for the following tests: multichannel automated liver function tests, serum sodium, AFP, albumin, creatinine, and coagulation panels
 
Blood sample will be drawn for HLA typing
 
Blood sample for NIDDK Biosample Repository
 
Whole blood for NIDDK Genetics Repository
 
Quality of life baseline assessment
 
HCV-infected subjects will undergo the following laboratory assessments in addition to those listed above: 
 
HCV RNA quantitative or qualitative assay
 
HCV genotype (if not done previously)
 
 
 
Subjects with HCC will also undergo the following imaging studies if not done within
 

389 390 391	
 
3 months previous to study enrollment:
 
o Bone scan
 
o Chest CT
 

392	
 
Abdominal MRI/contrast CT
 

393	
394	Pre-transplant Interval Assessments – Recipients:
395	
396	The following assessments will be performed quarterly from the time of enrollment until
397	transplant (or subject death if it occurs prior to transplant):
398	
399	• Physical examination: including weight, blood pressure, etc.

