468 469 470 471 472 473 474 475 476 477	
 
Physical examination: including weight, blood pressure, etc.
 
Routine laboratory assessment: blood will be drawn to obtain values for the following tests: multichannel automated liver function tests, serum sodium, albumin, AFP, creatinine, and coagulation panels
 
Blood sample for NIDDK Biosample Repository
 
Quality of life interval assessments at 3, 6, and 12 months and annually thereafter
 
Liver MRI/contrast CT at Month 3 only.
 
Recipients of a DDLT from an HCV-antibody positive donor must have HCV genotyping done at 3 months post-transplant
 

478 479	Post-transplant Interval Assessments – HCV-infected Recipients:
480	In addition to the assessments listed above, HCV-infected recipients will undergo the following assessments at the following time points:

483	• Week 1, Month 1, Month 3, Year 1, 2, and 3: HCV RNA quantitative or qualitative
484	analysis
485	• Month 3, Year 1, 2 and 3: Liver biopsy
486	• Month 3, Year 1, 2 and 3: Tissue sample for NIDDK Biosample Repository
487	
488	Post-transplant Interval Assessments – Subjects with HCC:
489	
490	In addition to the assessments listed above for all recipients, recipients with HCC will
491	undergo the following assessments at Months 6, 12, 18 and 24:
492	
493	• Serum AFP (at month 18 in addition to AFP's done at interval assessments for all
494	recipients)
495	• Abdominal MRI/contrast CT: at months 6, 12 and 24 only.
496	
497	Subjects Showing Signs and Symptoms of Allograft Rejection:
498	
499	Subjects showing signs and symptoms of allograft rejection will undergo a liver biopsy
500	with analysis to confirm the diagnosis of rejection. A biopsy will be performed to
501	confirm each rejection episode. A tissue sample from these biopsies will also be sent for
502	storage at the NIDDK Biosample Repository.
503	
504	Post-Donation Assessments – Donors:
505	
506	The following assessments will be performed for donors at Week 1, and Months 1, 3, and
507	12, and annually thereafter until the study is complete or the donor reaches a study
508	endpoint or is lost to follow-up:
509	
510	• Routine laboratory assessment: blood will be drawn to obtain values for the
511	following tests: multichannel automated liver function tests, albumin, creatinine,
512	coagulation panels, white blood cell count, hemoglobin, ferritin, platelets, BUN
513	Blood sample for NIDDK Biosample Repository
514	• Liver MRI/contrast CT at month 3 only

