#### 572 **4.1.4. Sample Size and Power Calculations**

573 We will compare the survival experience between those who receive an LDLT and those considered for an LDLT but not receive one. Although the analysis will involve a fairly 574 575 complex method of matching LDLT recipients with sets of non-recipients, for the 576 purpose of power calculations, we will assume a much simpler 2-group design. For this 577 analysis, we will pool the patients from the Retrospective Study and the Cohort Study for 578 maximum power. We anticipate having at least 300 LDLT recipients and 500 non-LDLT 579 recipients from the Retrospective Study, and 360 LDLT and 710 non-LDLT from the 580 Cohort Study, for a total of 660 LDLT and 1210 non-LDLT recipient patients. Power 581 calculations are based on the (two-sided) logrank test, an exponential survival 582 distribution, approximately uniform accrual of patients for at least 7 years (from 1998) 583 with 3 additional years of follow-up, 1% loss to follow-up, and a significance level of 584 0.05. Assuming a one-year survival probability of 0.875 in the LDLT group, we have 585 90% power to detect as significant a one-year survival probability among non-recipients 586 lower than 0.85 or higher than 0.90.

[figure not shown]

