#### 1434 4.6.5. Statistical Analysis

1435 Initial analysis of HCC will be primarily descriptive. The characteristics of HCC patients 1436 described will include TNM explant pathologic stage, use of ablation pre-transplant, and 1437 pre transplant ablation method (i.e. chemoembolization, RFA, etc.). The proportion of 1438 HCC recurring within one year will be presented, with 95% CI. Predictors of one-year 1439 recurrence will be explored using logistic regression for patients with at least one year of 1440 follow-up. The difference between recurrence (or presence) proportions for LDLT versus 1441 non-LDLT patients will also be estimated using a 95% confidence interval. A comparison 1442 of survival between these two groups will be performed using Cox regression, adjusted 1443 for various prognostic covariates. A comparison of survival between LDLT and 1444 deceased donor transplant recipients will also be performed. 1445 Secondary outcomes include comparisons of numbers of ablative procedures for LDLT 1446 versus waiting for DDLT, and numbers of surgical complications for LDLT versus 1447 DDLT. Differences in numbers of ablative procedures will be analyzed using Poisson 1448 regression, assuming that multiple ablative procedures may be necessary for some 1449 patients. Differences in surgical complications will be analyzed using logistic regression,

- 1450 assuming each complication either does or does not occur for each patient in a given time 1451 frame
- 1452 1453

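### Donor morbidity is planned as a plain proportion with no denominator rule although donor follow-up is unequal; complications after discharge would be better reported as cumulative incidence

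*Protocol*

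**What the plan says.** Section 4.3.5 (Primary Aim 3) treats the two donor outcomes differently. If any donor dies, "probability of mortality will be estimated using the Kaplan-Meier estimator with" confidence intervals at points such as one and two years. For complications, "Donor morbidity will be estimated as a proportion of donors with each reported" complication at relevant times after surgery, with a confidence interval for each proportion. The complications named are bile leak, primary non-function, graft failure, pneumonia and urinary tract infection, plus anything that requires admission, re-operation or other intervention. That last category has no end to its risk window.

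The precision statement is in section 4.2.4, which uses binomial intervals: "Assuming 660 donors, 95% CI widths" are to be at most ±0.04.

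Follow-up differs between donors. Under Post-Donation Assessments in section 4, visits continue "annually thereafter until the study is complete or the donor reaches a study" endpoint or is lost to follow-up. Subjects from the Retrospective Study "will join the cohort visit schedule from whatever clinical point they are at in their transplant or donation experience". Appendix B schedules donor visits to month 60.

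Elsewhere the protocol does allow for incomplete follow-up. Section 4.2.5 offers Cox regression for recipient complications that are times to event. In section 4.6.5, predictors of one-year HCC "recurrence will be explored using logistic regression for patients with at least one year of" follow-up.

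**The concern.** If donors who have not been followed to a given time stay in the denominator, they count as free of the complication, so the estimate can only be too low. Donors who donate late in the study, or who are lost, create this situation for any event that can occur months or years after discharge.

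Primary Aim 3 concerns short- and long-term health after donation. Section 4.3 lists biliary complications and other long-term consequences of hepatic resection among the open questions, and calls the answers critical to informed consent. An estimate that errs towards making donation look safer errs in the wrong direction for that use. The paragraph on donor death shows that a censoring-aware estimator was already in mind.

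**Working it through.** **1. The protocol's own figure.** With 660 donors and a proportion of 0.5, the half-width is 1.96 × √(0.25/660) = 0.038 (0.039 by the exact method). The ±0.04 in section 4.2.4 is correct for 660 fully observed donors.

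**2. Inputs for an illustration.** The protocol gives no accrual pattern or loss rate for donors. I borrow the Aim 1 recipient values in section 4.1.4: "approximately uniform accrual of patients for at least 7 years (from 1998"), then 3 more years of follow-up, and 1% loss. Section 4.1.4 does not say that the 1% is yearly; I assume so. My other assumptions are yearly losses of 5% and 10%, a true 5-year risk of 10%, a constant hazard and independent censoring.

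**3. Reading when all donors are the denominator.**
- Hazard h = −ln(0.9)/5 = 0.0211 per year.
- With yearly loss l, the probability of still being followed at t years is C(t) = (1 − l)^t up to 3 years, and (1 − l)^t × (10 − t)/7 from 3 to 10 years.
- The expected reading at time T is the integral from 0 to T of h·exp(−ht)·C(t).

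| Yearly loss | Relative shortfall at 1 y | 2 y | 3 y | 5-year reading of a true 10% |
|---|---|---|---|---|
| 1% | 0.5% | 1.0% | 1.5% | 9.2% |
| 5% | 2.5% | 4.9% | 7.2% | 8.4% |
| 10% | 5.1% | 9.8% | 14.1% | 7.5% |

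The 5-year relative shortfalls are about 8%, 16% and 25%.

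**4. Reading when only fully followed donors are the denominator.** At 1% loss, 660 × (5/7) × 0.99^5 = 448 donors are followed to 5 years. The half-width at a 10% risk is 1.96 × √(0.09/448) = 0.028. For 1 − Kaplan-Meier on all 660, the Greenwood variance is 0.9² × the integral from 0 to 5 of h/(660·exp(−ht)·C(t)). This gives a half-width of 0.024, equivalent to about 598 fully followed donors.

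**5. Sensitivity at 1% yearly loss.**
- *Later accrual.* Take 300 donors accrued evenly up to the "end of the Retrospective Study (2/28/2003) and the start of this prospective study at each" site, that is, by 2/28/2003 (5.16 years from 1998), and 360 over the remaining 1.84 years. The 5-year reading is then 8.7%, and about 276 donors are fully followed to 5 years.
- *Early events.* If 80% of events fall in the first 3 months (total risk 20%), the 5-year relative shortfall is only about 2%.

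**6. Scale.** The sampling half-width for a 10% risk in 660 donors is 1.96 × √(0.09/660) = 0.023. At 1% loss the 5-year bias of 0.008 is about a third of that. For a true 10% risk at 1 or 2 years the reading would be 9.95% or 9.90%, a bias of at most 0.001.

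**The case against.** The strongest reply is that the protocol does not commit to the biased version. Section 4.3.5 speaks of relevant times, not every time, and names no denominator. A proportion at a given time can be read as one among donors followed that long, which is unbiased under independent censoring. The 660 in section 4.2.4 is a planning figure, in a protocol that openly simplifies its sample size calculations. All of this stands. It limits the point to an unstated denominator, but it does not restore the precision that the fully followed version gives up.

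The size is also modest. The only times named in section 4.3.5 are one and two years, for mortality, and there the effect is negligible at low loss. Most of the named complications are perioperative, and surgical events cluster early. Section 4.3.1 plans against donor loss with tracking, regular reports and payment for visits from month 12. This stands too. The larger figures above depend on assumed loss rates and on a 5-year horizon that the protocol does not name for morbidity.

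A reader might infer from the late entry of Retrospective Study donors that their earlier complications go unrecorded. The documents do not show that. The sentence on joining concerns the visit schedule, and section 4 says that data before enrollment are collected retrospectively. Its wording, from the time of listing, fits recipients best, but nothing says that donors' earlier events are lost.

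**Conclusion.** The point holds as a low-severity improvement. Section 4.3.5 pairs a plain proportion and no denominator rule with an open-ended complication category and unequal follow-up. Cumulative incidence does better on either reading of the denominator: it removes the bias if all donors are counted, and it gains precision if only fully followed donors are.

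Using Kaplan-Meier for death and a proportion for morbidity may look like a contradiction. It is not one, because a plain proportion suits perioperative events. Nor do the documents support saying that the protocol fixes 660 as the analysis denominator, or that it will publish understated 5-year morbidity.

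The sizes in the working are illustrations. They rest on recipient accrual applied to donors, a constant hazard, independent censoring and a 1% loss read as yearly.

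**What to change.** In section 4.3.5, keep plain proportions of all donors for in-hospital and other perioperative complications. For complications after discharge, report the cumulative incidence of first occurrence at stated times, such as 3 months and 1, 2 and 3 years, and later if follow-up allows. Use 1 − Kaplan-Meier, or Aalen-Johansen if a donor dies, with 95% intervals and numbers at risk. Use delayed entry for Retrospective Study donors only if their earlier events turn out not to be captured.

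The cost is one or two sentences and slightly more programming. It needs complication dates, for which the donor post-surgical morbidity and hospitalization data in section 4.3.3 are the natural source; the forms themselves are not shown. Late estimates may look less favourable, and their intervals wider, than a crude proportion of 660 would suggest.
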